4.5.3 Dose Reductions

4.5.3.1 Nivolumab or Ipilimumab

There will be no dose reductions for nivolumab or ipilimumab.

4.5.3.2 EXTREME Regimen

This section includes information on dose modifications for cetuximab, cisplatin or carboplatin and 5-FU treatment related toxicities.

A maximum of 2 dose reductions per study drug are permitted; if additional reductions are required, that particular study drug must be discontinued. Once a dose has been decreased, it should remain reduced for all subsequent dosing unless dose is further reduced. No dose escalations will be allowed. If one of the study drugs is delayed due to drug related toxicities during a treatment cycle, the other study drugs in the regimen may be administered at the discretion of the investigator; when dosing is resumed, dose reduction should only be applied to the study drug that was withheld.

Participants who discontinue one of the study drugs may, at the investigators discretion continue administration of the other study drugs in the regimen.

For Cetuximab: Dose modifications are permitted, as follows:

Infusion Reactions:

- Reduce the infusion rate by 50% for NCI CTC Grade 1 or 2 and non-serious NCI CTC Grade 3 infusion reactions.
- Immediately and permanently discontinue cetuximab for serious infusion reactions, requiring medical intervention and/or hospitalization.
- See [Section 4.5.8.2](#) for treatment of Cetuximab Infusion Reactions.

Dermatologic Toxicity: Table 4.5.3.2-1 contains the recommended dose modifications for severe (CTCAE v4 Grade 3 or 4) acneiform rash.

Table 4.5.3.2-1: Cetuximab Dose Modification Guidelines for Rash			
Severe Acneiform Rash	Cetuximab	Outcome	Cetuximab Dose Modification
1 st Occurrence	Delay infusion 1 to 2 weeks	Improvement No Improvement	Continue at 250 mg/m ² Discontinue Cetuximab
2 nd Occurrence	Delay infusion 1 to 2 weeks	Improvement No Improvement	Continue at 200 mg/m ² Discontinue Cetuximab
3 rd Occurrence	Delay infusion	Improvement	Continue at 150 mg/m ²

Table 4.5.3.2-1: Cetuximab Dose Modification Guidelines for Rash			
Severe Acneiform Rash	Cetuximab	Outcome	Cetuximab Dose Modification
	1 to 2 weeks	No Improvement	Discontinue Cetuximab
4 th Occurrence	Discontinue Cetuximab permanently		

For Cisplatin, Carboplatin and 5-FU:

Recommendations for dose modifications for cisplatin, carboplatin and 5-FU should be considered with local institutional standards. The dose levels for 5-FU, cisplatin and carboplatin are listed in Table 4.5.3.2-2:

Table 4.5.3.2-2: Dose Levels for 5-FU, Cisplatin, and Carboplatin

	5-FU Dose	Cisplatin Dose	Carboplatin Dose
Starting Dose	1000 mg/m ²	100 mg/m ²	AUC 5.0
Dose Level -1	750 mg/m ²	75 mg/m ²	AUC 4.0
Dose Level -2	560 mg/m ²	56 mg/m ²	AUC 3.0

4.5.3.2.1 Recommended Dose Modifications for Hematologic Toxicity

Dose adjustments are based on nadir blood counts since the preceding chemotherapy administration. Dose level adjustments are relative to that of the preceding administration, and are described in Table 4.5.3.2-3

Table 4.5.3.2-3: 5-FU, Cisplatin, and Carboplatin Dose Modifications for Hematologic Toxicity^a

Drug Related Toxicity	5-FU	Cisplatin	Carboplatin
Neutrophils (ANC) < 500/mm ³ lasting ≥ 5 days	Decrease by -1 dose level	Decrease by -1 dose level	Decrease by -1 dose level
Febrile neutropenia (body temperature ≥ 38.5°C and ANC < 1,000/mm ³)	Decrease by -1 dose level	Decrease by -1 dose level	Decrease by -1 dose level
Platelets < 25,000/mm ³	Decrease by -1 dose level	Decrease by -1 dose level	Decrease by -1 dose level
Platelets < 50,000/mm ³ with significant bleeding or requiring blood transfusion	Decrease by -1 dose level	Decrease by -1 dose level	Decrease by -1 dose level
Grade 4 hemoglobin (< 6.5 g/100 mL)	Decrease by -1 dose level	Decrease by -1 dose level	Decrease by -1 dose level

^a If considered in the best interest of the participant, and consistent with local practice, investigators may decide to use supportive measures/treatment, and/or secondary prophylaxis instead of dose reductions for the next cycle.

Also, if toxicity can clearly be attributed to one of the drugs, the investigator may choose to only dose reduce one of the cytotoxics

4.5.3.2.2 Recommended Dose Modifications for Non-hematologic Toxicity

Dose adjustments for non-hematologic toxicity during treatment are described in Table 4.5.3.2-4. All dose modifications should be made based on the worst grade toxicity per CTCAE v4.0.

Table 4.5.3.2-4: 5-FU, Cisplatin, and Carboplatin Dose Modifications for Non-hematologic Toxicity^a

Drug Related Toxicity	5-FU	Cisplatin	Carboplatin
Nausea/vomiting ≥ Grade 3 despite optimal medical treatment	Decrease by -1 dose level	Decrease by -1 dose level	Decrease by -1 dose level
Stomatitis ≥ Grade 3	Decrease by -1 dose level	Decrease by -1 dose level	Decrease by -1 dose level
Diarrhea ≥ Grade 3 despite optimal medical treatment	Decrease by -1 dose level	Decrease by -1 dose level	Decrease by -1 dose level
Neuropathy (sensory or motor), Grade 2 lasting > 7 days OR Grade 3 lasting < 7 days	No modification	Decrease to -2 dose level	No modification
Neuropathy Grade 4 (sensory or motor)	No modification	Discontinue	No modification
Nephrotoxicity (Creatinine Clearance 50-59mL/min or Grade 3 Creatinine)	No modification	Decrease to -2 dose level or according to local practice	No modification
Total bilirubin > 1.5 x ULN	50% of previous dose	No modification	No modification
Total bilirubin > 2.5 x ULN	25% of previous dose	No modification	No modification
Total bilirubin > 4.0 x ULN	Discontinue	No modification	No modification
Other Grade ≥ 3 toxicities (except fatigue and transient arthralgia and myalgia)	Decrease by -1 dose level	Decrease by -1 dose level	Decrease by -1 dose level

^a If considered in the best interest of the participant, and consistent with local practice, investigators may decide to use supportive measures/treatment, and/or secondary prophylaxis instead of dose reductions for the next cycle. Also, if toxicity can clearly be attributed to one of the drugs, the investigator may choose to only dose reduce one of the cytotoxics.

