- One exception to note is when ipilimumab and nivolumab doses are delayed due to drug-related Grade ≥ 3 amylase or lipase abnormalities not associated with symptoms or clinical manifestations of pancreatitis. If the investigator assesses the Grade ≥ 3 amylase or lipase abnormality to be related to ipilimumab and not related to nivolumab, nivolumab may be resumed when the amylase or lipase abnormality resolves to Grade < 3 but ipilimumab may only be resumed when the amylase or lipase abnormality resolves to Grade 1 or baseline. Investigator attribution of this toxicity to the ipilimumab dosing must be clearly noted in the participant's medical chart. The BMS Medical Monitor should be consulted prior to resuming nivolumab in such participants.

4.5.4.3 **Criteria to Resume Chemotherapy Dosing (Arm B)**

Participants may resume treatment with study drug when the drug-related AE(s) resolved or returned to baseline value, with the following exceptions below.

- Participants may resume treatment in the presence of ANC $\geq 1500 / \text{mm}^3$ and Platelets $\geq 100 \times 10^3 / \mu\text{L}$
- Participants may resume treatment in the presence of Grade 2 fatigue.
- Participants who have not experienced a Grade 3 drug-related skin AE may resume treatment in the presence of Grade 2 skin toxicity.
- Participants with baseline Grade 1 AST/ALT or total bilirubin who require dose delays for reasons other than a 2-grade shift in AST/ALT or total bilirubin may resume treatment in the presence of Grade 2 AST/ALT OR total bilirubin.
- Participants with combined Grade 2 AST/ALT AND total bilirubin values meeting discontinuation parameters (Section 4.5.5.3) should have treatment permanently discontinued.
- Drug-related pulmonary toxicity, diarrhea, or colitis, must have resolved to baseline before treatment is resumed.
- For Cetuximab:
 - Pulmonary Toxicity: Permanently discontinue for confirmed interstitial lung disease.
 - Skin Reaction: If a participant experiences a Grade 3 skin reaction, cetuximab therapy is to be withheld for up to 2 consecutive infusions; the dose level should not be changed. The investigator can also consider concomitant treatment with topical and/or oral antibiotics; topical corticosteroids are not recommended. If the toxicity resolves to Grade 2 or less within 2 weeks, treatment may resume. For repeat occurrences of a Grade 3 skin reaction, see Table 4.5.3.2-1 above.

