4.5.5.3 EXTREME Regimen Dose Discontinuation (Arm B)

Treatment should be permanently discontinued for the following:

- Any drug-related Grade 4 toxicity including laboratory abnormalities the subject will be discontinued from the relevant study drug, with the following exceptions:
 - Isolated Grade 4 electrolyte abnormalities not associated with clinical sequelae and are adequately managed and corrected within 72 hours of onset.
 - Grade 4 neutropenia or lymphopenia ≤ 7 days
- Any Grade 3 non-skin, drug-related adverse event lasting > 7 days, with the following exceptions:
 - Grade 3 drug-related laboratory abnormalities do not require treatment discontinuation, except for the following scenarios:
 - ◆ Grade 3 drug-related thrombocytopenia associated with bleeding
 - ◆ Any of the following drug-related liver function test (LFT) abnormalities:
 - AST or ALT > 8 x ULN
 - Total bilirubin > 5 x ULN
 - Concurrent AST or ALT > 3 x ULN and total bilirubin > 2 x ULN
 - ◆ Calculated creatinine decreases to < 60 mL/min based on Cockcroft Gault formula on participants receiving cisplatin. Switch to carboplatin is allowed at the discretion of investigator for the remaining cycles. See re-treatment criteria [section 4.5.4.3](#)
 - Any dosing delay lasting > 6 weeks, with the following exceptions:
 - If local standards allow dosing delays > 6 weeks for drug-related AEs, contact the BMS Medical Monitor prior to re-initiating treatment.
 - Dosing delays > 6 weeks that occur for non-drug-related reasons may be allowed if approved by the BMS Medical Monitor. Prior to reinitiating treatment in a participant with a dosing delay lasting > 6 weeks, the BMS Medical Monitor must be consulted. Tumor assessments should continue as per protocol even if dosing is delayed.
- Any adverse event, laboratory abnormality, or intercurrent illness which, in the judgment of the Investigator, presents a substantial clinical risk to the participant with continued treatment.

Participants who discontinue one of the study drugs in Arm B may, at the investigators discretion, continue administration of the other study drugs. For example, if 5-FU is discontinued, cetuximab and platinum agent may be continued at the intended dose and schedule.

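### Arm B cisplatin at clearance 50-59 mL/min: the dose-modification table continues it at level -2, while the mandatory stop list and the eligibility text rule it out below 60

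*Protocol*

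**What the plan says.** Protocol Table 4.5.3.2-4 (Section 4.5.3.2.2) has one renal row, labelled "Nephrotoxicity (Creatinine Clearance 50-59mL/min or Grade 3 Creatinine" (closing bracket omitted here). Its cisplatin entry is "Decrease to -2 dose level or according to local practice"; 5-FU and carboplatin are unchanged. Footnote a, where judged best for the participant and in line with local practice, adds that "investigators may decide to use supportive measures/treatment, and/or secondary prophylaxis instead of dose reductions for the next cycle".

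Section 4.5.5.3, the list of reasons for permanent discontinuation in Arm B, includes "Calculated creatinine decreases to < 60 mL/min based on Cockcroft Gault formula on participants receiving cisplatin", followed by "Switch to carboplatin is allowed at the discretion of investigator for the remaining cycles". That bullet sits under "Grade 3 drug-related laboratory abnormalities do not require treatment discontinuation, except for the following scenarios", which is itself an exception to "Any Grade 3 non-skin, drug-related adverse event lasting > 7 days, with the following exceptions".

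Three other places bear on the point:

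- Section 3.5 says participants must stop investigational product for the reasons set out in Section 4.5.5. Section 4.1 lists cisplatin as investigational product.
- The Synopsis exclusion criteria and Section 3.3.2 (criterion 3.c.viii) set the entry floor at 50 mL/min and advise against cisplatin under 60.
- Section 4.5.1.2 substitutes carboplatin AUC 5 when cisplatin causes intolerable toxicity, and names renal impairment as an example.

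**The concern.** The table and the stop list give different default actions for the same laboratory value. A site that works from the table reduces the dose and carries on with cisplatin. A site that works from 4.5.5.3 stops it and may switch to carboplatin. Creatinine is checked within 72 hours before Day 1 of each Arm B cycle (Table 5.1-2, Section 5.3), so sites meet this decision in routine care.

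At stake are the renal safety of control-arm participants and uniform handling across sites. The eligibility text makes the mismatch plain: someone who enters at 55 mL/min should not be given cisplatin, yet someone who drops to 55 on cisplatin continues it under the table.

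**Working it through.** No design figure is involved, so the check sets the rules side by side.

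**Inputs**

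- Table 4.5.3.2-4: clearance 50-59 mL/min leads to cisplatin level -2, or local practice.
- Table 4.5.3.2-2: cisplatin starting dose 100, level -1 75, level -2 56 mg/m2.
- Section 4.5.5.3: clearance below 60 mL/min on cisplatin leads to a stop, with carboplatin allowed.
- Synopsis and Section 3.3.2: no cisplatin below 60 mL/min.

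**Step 1, thresholds.** The upper end of the table's band is 59, and 59 < 60. Every value in the band is therefore below the stop threshold, and no clearance triggers the reduction without also crossing it.

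**Step 2, dose for that cycle.** The table default is 56 mg/m2 and 4.5.5.3 gives 0, so the difference is 56 - 0 = 56 mg/m2. Later cycles depend on clearance and delays, so no cumulative figure follows.

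**Step 3, the nesting of the 4.5.5.3 bullet.** Its position leaves two readings.

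- *Free-standing:* any fall below 60 on cisplatin is a stop. The 50-59 part of the row contradicts it directly.
- *Limited to Grade 3 laboratory events:* the stop then meets only the Grade 3 creatinine part of the row, when clearance is also below 60. The eligibility text still contradicts the 50-59 part.

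The row is in conflict with other text on both readings. Section 4.5.4.3 suggests that the nesting is not a strict grade limit, because it applies parameters from the same nested list to Grade 2 liver values: "Participants with combined Grade 2 AST/ALT AND total bilirubin values meeting discontinuation parameters (Section 4.5.5.3) should have treatment permanently discontinued". That sentence concerns liver tests, so carrying it over to the renal bullet is an inference.

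**Step 4, delay and resume rules.** Section 4.5.2.2 requires a delay for Grade 3 laboratory abnormalities but names no clearance threshold. A value of 50-59 that is not Grade 3 is delayed only if the investigator so judges. Section 4.5.5.3 refers to 4.5.4.3 for re-treatment; that section asks for resolution or return to baseline and states no clearance value. Neither rule settles what to do at 50-59.

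**Step 5, is the table's silence on stopping deliberate?** Other rows say outright when a drug is to stop: cisplatin for Grade 4 neuropathy, 5-FU for bilirubin above 4.0 x ULN. The renal row does not.

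**Step 6, the SAP.** Section 7.4.2.4 tabulates Arm B dose reductions with reasons, and Section 7.3.1 tabulates reasons for stopping study treatment. The partial-discontinuation summary in Section 7.4.2.6 covers ipilimumab only, so a stop of cisplatin alone may be hard to see. Nothing in the SAP standardises the decision.

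**The case against.** The strongest reply is that the protocol already ranks the two rules. Section 3.5 makes the Section 4.5.5 reasons obligatory, whereas the table is headed as recommended, Section 4.5.3.2 ties it to local standards, and the cell itself allows local practice. A reader might infer that nothing says which section prevails; Section 3.5 shows otherwise. The ranking stands, but it does not remove the conflict. A site reading the table alone still finds continued cisplatin as the named action, with no pointer to 4.5.5.3.

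A second reply is that the table works from the worst toxicity grade, so level -2 may be the dose after recovery. That is a fair reading of the Grade 3 creatinine half, where a delay and resolution or return to baseline are required. It does not rescue the 50-59 half. No delay is mandated there, and the 4.5.5.3 criterion is triggered by the fall itself.

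A reader might also take footnote a to permit an unreduced 75 or 100 mg/m2 at 50-59 mL/min. The documents do not support that as the size of the problem. The footnote applies only if it serves the participant and fits local practice, and using it this way would mean disregarding the stop rule and the eligibility text. Only the 56 mg/m2 default follows from the row.

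**Conclusion.** The inconsistency is real and minor. For clearance 50-59 mL/min on cisplatin, the table's default (56 mg/m2) contradicts the stop rule and the eligibility text (0, with carboplatin available). The table row is the outlier. The documents do not say how often this would arise.

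The conclusion rests on two readings. The first is that the 4.5.5.3 bullet means creatinine clearance: it says creatinine, but the mL/min unit and the Cockcroft-Gault formula leave little doubt. The second is that the advice against cisplatin below 60, although placed among the screening criteria, is not confined to entry; its wording sets no such limit.

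Two stronger conclusions might be inferred and are not supported. Grade 3 creatinine with clearance at or above 60 is not a stop criterion in 4.5.5.3, so requiring a stop there would be a new rule. The point also does not reach the primary analysis: overall survival, alpha and power are unaffected.

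**What to change.** 1. **Table 4.5.3.2-4.** Split the nephrotoxicity row. For clearance < 60 mL/min (Cockcroft-Gault), set the cisplatin entry to *Discontinue cisplatin; switch to carboplatin permitted (see 4.5.5.3)* and state that footnote a does not apply. This also covers clearance below 50, which the table does not list. Leave Grade 3 creatinine with clearance >= 60 at level -2 after the required delay and recovery.
2. **Section 4.5.5.3.** Move the < 60 mL/min criterion out of the Grade 3 laboratory list so that it stands alone, keep it limited to drug-related falls, and change *Calculated creatinine* to *Calculated creatinine clearance*.

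The cost is one row split and one bullet moved and reworded. Because it changes dosing instructions, it should go through a protocol revision with IRB/IEC review under Section 9.1.1, with a memo to sites. No visits, procedures or analyses are added. The practical benefit depends on participants still being in their platinum cycles, which the documents do not state.

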4.5.4 Criteria to Resume Dosing

4.5.4.1 Criteria to Resume Nivolumab Dosing (Arm A)

Participants may resume treatment with nivolumab when the drug-related AE(s) resolve(s) to Grade ≤ 1 or baseline, with the following exceptions:

- Participants may resume treatment in the presence of Grade 2 fatigue.

- Participants who have not experienced a Grade 3 drug-related skin AE may resume treatment in the presence of Grade 2 skin toxicity.
- Participants who received systemic corticosteroids for management of any drug-related toxicity must be off corticosteroids or have tapered down to an equivalent dose of prednisone ≤ 10 mg/day.
- For participants with Grade 2 AST, ALT and/or Total Bilirubin Abnormalities, dosing may resume when laboratory values return to baseline and management with corticosteroids, if needed, is complete.
- Drug-related pulmonary toxicity, diarrhea, or colitis must have resolved to baseline before treatment is resumed. Participants with persistent Grade 1 pneumonitis after completion of a steroid taper over at least 1 month may be eligible for retreatment if discussed with and approved by the BMS Medical Monitor.

Participants with drug-related endocrinopathies adequately controlled with only physiologic hormone replacement may resume treatment after consultation with the BMS Medical Monitor (or designee). Adrenal insufficiency requires discontinuation regardless of control with hormone replacement.

4.5.4.2 Criteria to Resume Ipilimumab Dosing (Arm A)

Participants may resume treatment with nivolumab and ipilimumab when drug-related AE(s) resolve(s) to Grade 1 or baseline value, with the following exceptions:

- Participants may resume treatment in the presence of Grade 2 fatigue.
- Participants who have not experienced a Grade 3 drug-related skin AE may resume treatment in the presence of Grade 2 skin toxicity.
- Participants with baseline Grade 1 AST/ALT or total bilirubin who require dose delays for reasons other than a 2-grade shift in AST/ALT or total bilirubin may resume treatment in the presence of Grade 2 AST/ALT or total bilirubin.
- Participants with combined Grade 2 AST/ALT and total bilirubin values meeting discontinuation parameters ([Section 4.5.5.2](#)) should have treatment permanently discontinued.
- Drug-related pulmonary toxicity, diarrhea, or colitis must have resolved to baseline before treatment is resumed.
- Participants who received systemic corticosteroids for management of any drug-related toxicity must be off corticosteroids or have tapered down to an equivalent dose of prednisone ≤ 10 mg/day.
- Drug-related endocrinopathies adequately controlled with only physiologic hormone replacement may resume treatment after consultation with the BMS Medical Monitor.
- Dose delay of ipilimumab which results in no ipilimumab dosing for > 12 weeks requires ipilimumab discontinuation, with exceptions as noted in [Section 4.5.5.2](#).
- Ipilimumab may not be resumed sooner than 6 weeks (± 3 days) after the prior ipilimumab dose.
- In general, participants who meet criteria to resume ipilimumab will also have met criteria to resume nivolumab, so it should be feasible to synchronize dosing of both drugs when resuming

ipilimumab. In order to facilitate this, the dosing days of nivolumab and ipilimumab may be adjusted within the permitted ± 3 day window, as long as consecutive nivolumab doses are given at least 12 days apart.

- One exception to note is when ipilimumab and nivolumab doses are delayed due to drug-related Grade ≥ 3 amylase or lipase abnormalities not associated with symptoms or clinical manifestations of pancreatitis. If the investigator assesses the Grade ≥ 3 amylase or lipase abnormality to be related to ipilimumab and not related to nivolumab, nivolumab may be resumed when the amylase or lipase abnormality resolves to Grade < 3 but ipilimumab may only be resumed when the amylase or lipase abnormality resolves to Grade 1 or baseline. Investigator attribution of this toxicity to the ipilimumab dosing must be clearly noted in the participant's medical chart. The BMS Medical Monitor should be consulted prior to resuming nivolumab in such participants.

4.5.4.3 **Criteria to Resume Chemotherapy Dosing (Arm B)**

Participants may resume treatment with study drug when the drug-related AE(s) resolved or returned to baseline value, with the following exceptions below.

- Participants may resume treatment in the presence of ANC $\geq 1500 / \text{mm}^3$ and Platelets $\geq 100 \times 10^3 / \mu\text{L}$
- Participants may resume treatment in the presence of Grade 2 fatigue.
- Participants who have not experienced a Grade 3 drug-related skin AE may resume treatment in the presence of Grade 2 skin toxicity.
- Participants with baseline Grade 1 AST/ALT or total bilirubin who require dose delays for reasons other than a 2-grade shift in AST/ALT or total bilirubin may resume treatment in the presence of Grade 2 AST/ALT OR total bilirubin.
- Participants with combined Grade 2 AST/ALT AND total bilirubin values meeting discontinuation parameters (Section 4.5.5.3) should have treatment permanently discontinued.
- Drug-related pulmonary toxicity, diarrhea, or colitis, must have resolved to baseline before treatment is resumed.
- For Cetuximab:
 - Pulmonary Toxicity: Permanently discontinue for confirmed interstitial lung disease.
 - Skin Reaction: If a participant experiences a Grade 3 skin reaction, cetuximab therapy is to be withheld for up to 2 consecutive infusions; the dose level should not be changed. The investigator can also consider concomitant treatment with topical and/or oral antibiotics; topical corticosteroids are not recommended. If the toxicity resolves to Grade 2 or less within 2 weeks, treatment may resume. For repeat occurrences of a Grade 3 skin reaction, see Table 4.5.3.2-1 above.

If the criteria to resume treatment are met, the participant should restart treatment at the next scheduled time-point per protocol. If treatment is delayed > 6 weeks, the participant must be permanently discontinued from study therapy, except as specified in Section 4.5.5.3.

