4.5.2.1 Nivolumab and Ipilimumab (Arm A)

Dose delay criteria apply for all drug-related AEs. Treatment delay is up to 6 weeks for nivolumab and up to 12 weeks for ipilimumab from the last dose are allowable (any dose delays greater than these will require approval from the medical monitor). It is permissible in cases of a dose held due to AE to skip the dose in the cycle in order to bring the patient back on track with the next Cycle visit.

Tumor assessments for all participants should continue as per protocol even if dosing is delayed.

Nivolumab and ipilimumab administration should be delayed for the following:

- Grade 2 non-skin, drug-related AE, with the exception of fatigue
- Grade 2 drug-related creatinine, AST, ALT and/or Total Bilirubin abnormalities
- Grade 3 skin, drug-related AE
- Grade 3 drug-related laboratory abnormality, with the following exceptions:
 - Grade 3 lymphopenia or asymptomatic amylase or lipase does not require dose delay
 - Grade ≥ 3 AST, ALT, Total Bilirubin will require dose discontinuation (see section 4.5.5)
- Any adverse event, laboratory abnormality, or intercurrent illness which, in the judgment of the investigator, warrants delaying the dose of study medication.
- Participants receiving ipilimumab in combination with nivolumab that have drug-related toxicities that meet the criteria for dose delay, should have both drugs (ipilimumab and nivolumab) delayed until retreatment criteria are met. (Exceptions apply to the retreatment criteria after dose delay of ipilimumab and nivolumab for Grade ≤ 3 amylase and lipase

abnormalities that are not associated with symptoms or clinical manifestations of pancreatitis and that are attributed to ipilimumab alone.)

- Participants who require delay of nivolumab should be re-evaluated weekly or more frequently if clinically indicated and resume nivolumab dosing when re-treatment criteria are met.

Rescheduling:

- Nivolumab may be delayed until the next planned ipilimumab dose if the next ipilimumab dose is scheduled within the next 12 days. This will permit periodic ipilimumab dosing to be synchronized with nivolumab dosing.

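### For Arm A participants with baseline Grade 1 AST/ALT or bilirubin who rise to drug-related Grade 2, Protocol 4.5.4.2 permits re-dosing that 4.5.4.1 withholds until return to baseline

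*Protocol*

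**What the plan says.** **Hold.** Protocol 4.5.2.1 lists, among the reasons to delay both Arm A drugs, "Grade 2 drug-related creatinine, AST, ALT and/or Total Bilirubin abnormalities". It makes no exception for an abnormal baseline. Participants who meet delay criteria "should have both drugs (ipilimumab and nivolumab) delayed until retreatment criteria are met"; the exception stated there concerns amylase and lipase.

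**Restart, nivolumab section (4.5.4.1).** The liver bullet reads "For participants with Grade 2 AST, ALT and/or Total Bilirubin Abnormalities, dosing may resume when laboratory values return to baseline". It adds a second condition about steroids: "management with corticosteroids, if needed, is complete". There is no carve-out for a Grade 1 baseline.

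**Restart, ipilimumab section (4.5.4.2).** The heading names ipilimumab, but the lead sentence reads "Participants may resume treatment with nivolumab and ipilimumab when drug-related AE(s) resolve(s) to Grade 1 or baseline value", followed by exceptions. One exception is the point at issue. It applies to "Participants with baseline Grade 1 AST/ALT or total bilirubin who require dose delays for reasons other than a 2-grade shift", where the shift meant is in these liver tests, and it says that such people "may resume treatment in the presence of Grade 2 AST/ALT or total bilirubin". The next bullet removes "Participants with combined Grade 2 AST/ALT and total bilirubin values meeting discontinuation parameters" and sends them to permanent discontinuation; they are outside this point.

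Section 4.5.4.2 also says that participants who satisfy the ipilimumab criteria will generally have satisfied the nivolumab criteria too. The one mismatch it flags is asymptomatic Grade 3 or higher amylase or lipase. Liver tests are not mentioned there.

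**The concern.** A participant who enters with Grade 1 AST/ALT or bilirubin and rises to drug-related Grade 2 gets two different answers on restarting nivolumab. Sites acting in good faith could treat the same laboratory result differently.

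What is at stake is liver safety and consistent dosing. Protocol 1.6 names hepatitis among the common immune-mediated events of these agents and says that the combination is being evaluated in SCCHN for the first time in this study. If Grade 2 persists, the 4.5.4.1 route gives no nivolumab. Once the delay passes 6 weeks from the previous dose, 4.5.5.1 calls for discontinuation, subject to its exceptions, and does not let ipilimumab continue alone. The 4.5.4.2 route allows both drugs back while the value is still Grade 2.

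**Working it through.** The plan gives no figure to reproduce, so the check is to follow one participant through the rules.

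1. **Entry.** Protocol 3.3.2 excludes AST/ALT only above 3.0 x ULN (5 x ULN with liver metastases) and bilirubin only above 1.5 x ULN. Raised baseline values are therefore eligible, and 4.5.4.2 itself presupposes Grade 1 baselines.
2. **Event.** AST, ALT or bilirubin rises from Grade 1 to Grade 2 and is judged drug-related. The combined-elevation discontinuation criterion (AST or ALT > 3 x ULN with bilirubin > 2 x ULN) is not met.
3. **Hold, 4.5.2.1.** Both drugs stop.
4. **Restart, 4.5.4.1.** Nivolumab stays off until the value is back at baseline, here Grade 1, and steroid management is complete.
5. **Restart, 4.5.4.2.** The shift is 2 − 1 = 1 grade. The clause excludes only delays caused by a 2-grade shift, which from Grade 1 means Grade 3. A one-grade shift is therefore inside the permission, and both drugs may resume at Grade 2.
6. **Steroids.** Both sections carry a general bullet allowing restart at prednisone 10 mg/day or less. Only the 4.5.4.1 liver bullet asks for more, namely completion, and 4.5.4.2 does not repeat it.

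Steps 4 and 5 disagree about nivolumab, and neither section says which prevails.

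**Size.** The documents give no rate of baseline Grade 1 liver tests or of drug-related rises, so no count can be derived. For scale only:

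- Arm A = 930 / 2 = 465 participants.
- Each 1% of Arm A in this position = 0.01 × 465 = 4.65, about 5 participants.
- Nivolumab every 2 weeks falls due on days 14, 28 and 42 after the last dose, so 0 to 3 doses within 6 weeks turn on which section is followed.
- Ipilimumab every 6 weeks gives 42 / 42 = 1, so 0 to 1 dose in the same window.

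The lower ends apply if the value returns to baseline before the next due dose, and the upper ends only if Grade 2 lasts the full 6 weeks. Doses lost after a discontinuation are not counted.

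**The case against.** The best defence is structural. Nivolumab has its own restart section with a specific liver bullet, 4.5.4.2 is headed for ipilimumab, and its remark about meeting both sets of criteria treats the nivolumab criteria as a separate test. The clause says *may*, so it never compels a dose. It also has a natural use: a participant held for some other toxicity who happens to have a Grade 2 liver value.

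Part of this stands. The permission is optional, so following 4.5.4.1 complies with both sections, and the incidental-value reading is sensible. But the lead sentence of 4.5.4.2 names both drugs, and the clause excludes only a 2-grade shift, so it is not confined to incidental or unrelated values. If 4.5.4.2 is read as covering ipilimumab alone, ipilimumab could restart at Grade 2 while nivolumab waits. That sits badly with the joint hold in 4.5.2.1 and with the expectation that the two sets of criteria usually agree.

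A reader might infer more than the documents support:

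- **That a site must breach one section.** It need not, as noted above.
- **That both drugs are automatically lost at 6 weeks.** Section 4.5.2.1 allows longer delays after discussion with the Study Director or Medical Monitor, and 4.5.5.1 excepts prolonged steroid tapers.
- **That Arm B has the same conflict, because 4.5.4.3 repeats the clause.** Section 4.5.2.2 exempts laboratory abnormalities from its Grade 2 hold. Its bilirubin and AST/ALT line sits under the exceptions to the Grade 3 laboratory rule and can be read with the alkaline phosphatase condition applying to bilirubin as well. Section 4.5.2 also defers to local standards for EXTREME dose modifications. No Arm B conflict is established.
- **That the plan has no other restart rule.** The hepatic algorithm in Appendix 2 is a figure missing from the available text, so this cannot be checked.

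**Conclusion.** The inconsistency is real but narrow. It applies to Arm A participants with baseline Grade 1 AST/ALT or bilirubin who rise to drug-related Grade 2 without meeting the combined-elevation criterion. For them, 4.5.4.2 as worded permits re-dosing that 4.5.4.1 withholds.

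The number affected is unknown and likely small. Harm is limited by laboratory tests within 72 hours before each Arm A dose (Protocol 5.3), by the general requirement in 4.5.5.1 to discontinue nivolumab for drug-related Grade 3 or higher values (with a Medical Monitor discussion possible for Grade 3 AST/ALT), and by discontinuation for combined elevations. No endpoint, alpha, power or event count is touched.

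The conclusion rests on two readings of the text: that the 4.5.4.2 lead sentence means both drugs, as it says, and that a one-grade rise is a reason other than a 2-grade shift. It assumes no event rate. It is worth correcting because a safety rule should give one answer, and aligning the sections is cheap.

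**What to change.** 1. In 4.5.4.2, replace the baseline-Grade-1 clause with the 4.5.4.1 liver rule. After a hold for drug-related Grade 2 AST, ALT or bilirubin, both drugs resume only on return to baseline with any steroid management complete.
2. State separately that a Grade 2 value judged not drug-related (for example, from liver metastases), in a participant held for another reason, does not by itself bar resumption. Word the 4.5.4.1 liver bullet the same way. Simply limiting the existing clause to unrelated values would not work: its lead rule concerns drug-related events, so the exception would then except nothing.
3. Correct the 4.5.4.2 lead sentence to say which drug or drugs it governs.

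If the sponsor prefers the permissive rule for Grade 1 baselines, 4.5.4.1 should say so explicitly. Either way, one rule is needed.

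The cost is a protocol amendment, which needs IRB/IEC approval under Protocol 9.1.1. No procedures are added. The stricter rule means somewhat longer holds for a few participants, and possibly discontinuation where Grade 2 persists and no longer delay is agreed.
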